3.2.1 Efficacy Variables

3.2.1.1 Tumor Response according to RECIST v1.1

The anti-tumor activity of Pan-HER will be assessed according to RECIST, v 1.1 using CT or MRI. The use of CT or MRI must be consistent per patient throughout the trial.

Disease Status Evaluation by CT or MRI will occur at:

- Screening

Note: A CT/MRI performed within 28 days prior to Day 1 may be used for evaluation of eligibility and as baseline scan, provided that the CT/MRI has been performed according to the CTP requirements

- End of Cycle 2 and end of every second cycle thereafter, i.e. Cycle 4, 6, 8 etc.

Note: End of cycle assessments may be conducted at any time during the week prior to Day 1 of the next cycle

- After Suspected Progressive Disease (PD) (as soon as possible)
- Confirmation of response, to be performed 28 (+7) days after the first assessment of CR/PR

PAREXEL International
Statistical Analysis Plan Template for Early Phase Studies

Symphogen A/S

Sym013-01

- EOT (if >3 weeks since previous CT/MRI)
- At 1M FUP (if PD was not documented before or at EOT)

If PD is documented at any time, no further disease assessments will be required. Patients with documented PD will be discontinued from Pan-HER so that alternative management of their malignancy may be considered.

For all imaging time points, the following will be recorded as per RECIST v1.1: Target lesions including size, location, and type (nodal/non-nodal); sum of diameters of target lesions; any new lesions noted during trial, including size, location, and type (nodal/non-nodal); response assessment at each visit (PD, SD, PR, CR or Not Evaluable [NE]), per investigators evaluation.

Tumor evaluation according to RECIST 1.1 will be the basis for the derivation of all efficacy endpoints. To be assigned a status of confirmed PR or CR, changes in disease status must be confirmed by repeat imaging studies performed no less than 28 days (4 weeks) after the criteria for response are first met. In the case of SD, follow-up measurements must have met the SD criteria at least once after trial entry at a minimal interval in general no less than 6-8 weeks from first dose of Pan-HER; for the scope of derivation of SD as best overall response, a minimal SD duration of 6 week will be required.

The following anti-tumor response endpoints will be derived based on Tumor evaluation according to RECIST 1.1:

- Target and Non Target Response at each timepoint will be derived according to RECIST 1.1 [1].
 - Evaluation of target lesions will be derived based on sum of diameters as follow:
 - *'Complete Response (CR): Disappearance of all target lesions. Any pathological lymph nodes (whether target or non-target) must have reduction in short axis to <10 mm.*

PAREXEL International
Statistical Analysis Plan Template for Early Phase Studies

Symphogen A/S
Sym013-01

- *Partial Response (PR): At least a 30% decrease in the sum of diameters of target lesions, taking as reference the baseline sum diameters.*
- *Progressive Disease (PD): At least a 20% increase in the sum of diameters of target lesions, taking as reference the smallest sum on study (this includes the baseline sum if that is the smallest on study). In addition to the relative increase of 20%, the sum must also demonstrate an absolute increase of at least 5 mm. (Note: the appearance of one or more new lesions is also considered progression).*
- *Stable Disease (SD): Neither sufficient shrinkage to qualify for PR nor sufficient increase to qualify for PD, taking as reference the smallest sum of diameters while on study. ’*
- Evaluation of non-target lesions: non-target lesions response will be reported in CRF as CR, NON-CR/NON-PD, PD, Not Evaluated; worst response will be taken as the Non-Target Lesion response for the correspondent timepoint; for assessment of worst response the following order will be followed: PD, Not Evaluated, NON-CR/NON-PD, CR.

Target and Non-Target Response at each timepoint, derived as described, will be reviewed by Symphogen and PAREXEL on a patient by patient basis across time.

At each timepoint Overall Responses will be captured in CRF; as well Overall Responses will also be derived according to RECIST 1.1 [1]:

Table 1 of above-mentioned paper [1] is reported below and will be used to derive overall response at each time point for patients who have measurable disease at baseline. When patients have non-measurable (therefore non-target) disease only, Table 2 is to be used.

Overall responses derived as described are supposed to coincide with overall responses collected in CRF; cases of mismatch will be queried; any unsolved case of mismatch will be reviewed by Symphogen and PAREXEL on a patient by patient basis across time.

PAREXEL International
Statistical Analysis Plan Template for Early Phase Studies

Symphegen A/S
 Sym013-01

Table 1 – Time point response: patients with target (+/- non-target) disease.

Target lesions	Non-target lesions	New lesions	Overall response
CR	CR	No	CR
CR	Non-CR/non-PD	No	PR
CR	Not evaluated	No	PR
PR	Non-PD or not all evaluated	No	PR
SD	Non-PD or not all evaluated	No	SD
Not all evaluated	Non-PD	No	NE
PD	Any	Yes or No	PD
Any	PD	Yes or No	PD
Any	Any	Yes	PD

CR = complete response, PR = partial response, SD = stable disease, PD = progressive disease, and NE = inevaluable.

Table 2 – Time point response: patients with non-target disease only.

Non-target lesions	New lesions	Overall response
CR	No	CR
Non-CR/non-PD	No	Non-CR/non-PD ^a
Not all evaluated	No	NE
Unequivocal PD	Yes or No	PD
Any	Yes	PD

CR = complete response, PD = progressive disease, and NE = inevaluable.
 a 'Non-CR/non-PD' is preferred over 'stable disease' for non-target disease since SD is increasingly used as endpoint for assessment of efficacy in some trials so to assign this category when no lesions can be measured is not advised.

- Confirmed Best Overall Response (BOR) by RECIST v1.1.

Per RECIST 1.1[1]:

'the best overall response is the best response recorded from the start of the study treatment until the end of treatment taking into account any requirement for confirmation.'
'Specifically, in non-randomised trials where response is the primary endpoint, confirmation of PR or CR is needed to deem either one the 'best overall response'.' *'Best response determination in trials where confirmation of complete or partial response is*

PAREXEL International
Statistical Analysis Plan Template for Early Phase Studies

Symphogen A/S
Sym013-01

required: Complete or partial responses may be claimed only if the criteria for each are met at a subsequent time point as specified in the protocol (generally 4 weeks later). In this circumstance, the best overall response can be interpreted as in Table 3.'

Table 3 of above-mentioned paper [1] is reported below and will be used to derive confirmed Best Overall Responses. In this study a minimum SD duration of 6 week will be used as criterium to confirm SD as Best Overall Response.

Table 3 – Best overall response when confirmation of CR and PR required.

Overall response First time point	Overall response Subsequent time point	BEST overall response
CR	CR	CR
CR	PR	SD, PD or PR ^a
CR	SD	SD provided minimum criteria for SD duration met, otherwise, PD
CR	PD	SD provided minimum criteria for SD duration met, otherwise, PD
CR	NE	SD provided minimum criteria for SD duration met, otherwise NE
PR	CR	PR
PR	PR	PR
PR	SD	SD
PR	PD	SD provided minimum criteria for SD duration met, otherwise, PD
PR	NE	SD provided minimum criteria for SD duration met, otherwise NE
NE	NE	NE

CR = complete response, PR = partial response, SD = stable disease, PD = progressive disease, and NE = inevaluable.

a If a CR is truly met at first time point, then any disease seen at a subsequent time point, even disease meeting PR criteria relative to baseline, makes the disease PD at that point (since disease must have reappeared after CR). Best response would depend on whether minimum duration for SD was met. However, sometimes 'CR' may be claimed when subsequent scans suggest small lesions were likely still present and in fact the patient had PR, not CR at the first time point. Under these circumstances, the original CR should be changed to PR and the best response is PR.

Patients with non-target disease only, may have a time point response of NON-CR/NON-PD, these responses will be included in the count of SD.

Determinations of Best Overall Responses derived as described will be reviewed by Symphogen and PAREXEL on a patient by patient basis across time.

- Unconfirmed BOR by RECIST v1.1:

Per RECIST 1.1 [1]: in cases where confirmation of complete or partial response is not required the Best response is defined as the best response across all time points (for example, a patient who has SD at first assessment, PR at second assessment, and PD on last assessment has a best overall response of PR). When SD is believed to be best unconfirmed response, it must also meet the protocol specified minimum time from baseline.

PAREXEL International
Statistical Analysis Plan Template for Early Phase Studies

Symphegen A/S
Sym013-01

Patients with non-target disease only, may have a time point response of NON-CR/NON-PD, these responses will be included in the count of SD.

- Documented objective response (OR) confirmed and unconfirmed, based on determination of confirmed and unconfirmed best overall response (BOR) per RECIST v1.1.

Confirmed OR is defined as the percentage of patients who had confirmed CR or PR.

Unconfirmed OR is defined as the percentage of patients who had unconfirmed CR or PR.

'The duration of overall response is measured from the time measurement criteria are first met for CR/PR (whichever is first recorded) until the first date that recurrent or progressive disease is objectively documented (taking as reference for progressive disease the smallest measurements recorded on study). ' [1].

Duration of Response (weeks) = (Date of PD – Date of first CR/PR [whichever is first recorded] + 1) / 7

- Time to Progression (TTP)

Time to documented PD (based on radiological assessments) will be derived and expressed in the unit of weeks. TTP is defined as the time from first dose of study drug until objective tumor progression; TTP does not include deaths [3]. Based on this definition, PDs will be counted as outcome; patients with last tumor assessment showing CR or PR or SD will be censored at the time of last available tumor assessment per RECIST v1.1; patients who died for any cause (including deaths of disease but with no documented PD) will as well be censored at the time of last available tumor assessment per RECIST v1.1.

TTP (weeks) = (Date of PD – Date of first IMP infusion + 1) / 7

In this study, there is no planned survival status after discontinuation of study treatment, therefore, progression-free survival is not calculated.

PAREXEL International
Statistical Analysis Plan Template for Early Phase Studies

Symphogen A/S
Sym013-01

- Disease control rate (DCR), based on determination of confirmed BOR per RECIST v1.1.

The DCR is defined as the percentage of patients who had confirmed BOR of CR, PR or SD of at least 16 weeks. Definition of duration of TTP corresponds to SD duration; thus, these times will be used to determine if a patient was in SD for at least 16 weeks.

- Changes in sum of diameters of target lesions from baseline to end of trial participation

For patients with measurable disease (i.e., with target lesions), absolute and percent changes in the sum of diameters of target lesions from baseline to end of trial participation will be calculated, the best change will be identified as largest reduction or smallest increase.

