4.10.2.1 Anti-Tumor Response according to RECIST v1.1

The following anti-tumor response endpoints will be measured in Part 1:

- Confirmed and unconfirmed BOR by RECIST v1.1 will be listed and summarized by dose regimen and dose level received using frequency distribution for the categories CR, PR, SD, PD, and Not Evaluable.
- Number and percentage of patients with documented confirmed and unconfirmed OR will be summarized by dose regimen and dose level using frequency distribution with the corresponding 95% exact Clopper-Pearson Confidence Intervals (CI) for binomial proportion. All documented ORs will be listed including duration (weeks) of response.
- Patients in DCR will be listed and summarized by dose regimen and dose level using frequency distribution with the corresponding 95% exact Clopper-Pearson Confidence Intervals (CI) for binomial proportion.
- Time to Progression (TTP)

PAREXEL International
Statistical Analysis Plan Template for Early Phase Studies

Symphogen A/S
Sym013-01

The median TTP, as well as 26 weeks and 52 weeks TTP rates and the corresponding 95% CIs will be estimated using the product-limit method and presented using a Kaplan-Meier plot. Number and percent of censored patients will be presented, also number and percent of patients censored for death will be presented.

- Changes in sum of diameters of target lesions from baseline to end of trial participation
Changes in the sum of diameters of target lesions from baseline to end of trial participation will be listed as percentage and absolute value, the best change (i.e., largest reduction or smallest increase) will be identified and presented using summary table and plotted with a waterfall plot. Change in sum of diameters will also be presented by primary tumor type.
- Results of the tumor evaluation by CT/MRI for target lesions, non-target lesions and timepoint tumor response will be listed, as well as derived target and non-target time point responses.

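### The SAP counts Non-CR/Non-PD in patients with non-target disease only as stable disease, against the RECIST note it reproduces, and this passes into the added disease control rate

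*SAP*

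**What the plan says.** SAP 3.2.1.1 derives the response at each scan from two RECIST tables. For patients with target lesions, SD is a statement about the sum of diameters, "taking as reference the smallest sum of diameters while on study". For the rest, "When patients have non-measurable (therefore non-target) disease only, Table 2 is to be used". Table 2 has no SD outcome. Its possible results are CR, Non-CR/Non-PD, NE and PD. Its footnote prefers Non-CR/Non-PD to SD because trials increasingly use SD as an efficacy endpoint, "so to assign this category when no lesions can be measured is not advised".

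Under confirmed BOR, and again under unconfirmed BOR, the same section then states: "Patients with non-target disease only, may have a time point response of NON-CR/NON-PD, these responses will be included in the count of SD".

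The provisions that follow from it are:

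- SAP 3.2.1.1 on duration: "In this study a minimum SD duration of 6 week will be used as criterium to confirm SD as Best Overall Response".
- SAP 3.2.1.1 on DCR: "The DCR is defined as the percentage of patients who had confirmed BOR of CR, PR or SD of at least 16 weeks". The 16 weeks are judged by time to progression.
- SAP 4.14: DCR was not a protocol endpoint and was added in the SAP.
- SAP 4.10.2: efficacy endpoints use the Full Analysis Set (FAS), meaning all treated patients.
- SAP 4.10.2.1: BOR is summarised "using frequency distribution for the categories CR, PR, SD, PD, and Not Evaluable".
- SAP 3.2: documented OR is limited to patients with measurable disease. DCR carries no such limit.
- Protocol 6.1, criterion 8a: measurable disease is an entry requirement for Part 2 only. SAP 4.14 records that Part 2 did not take place.

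**The concern.** The SAP adopts a table that keeps Non-CR/Non-PD separate, prints the reason for doing so, and then merges the category into SD without explaining the departure. It also puts SD to the use the footnote warns about, because DCR is an efficacy endpoint built partly on SD.

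For a patient with target lesions, SD means that a measured sum neither shrank nor grew past set thresholds. For a patient with non-target disease only, it means that non-target lesions persisted without unequivocal progression and no new lesion appeared. These are different standards of evidence, and the planned BOR table shows them as one number. A reader of the SD count or DCR in Table 14.2.4.1 cannot tell how much of either comes from the qualitative standard.

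**Working it through.** The plan states no figure on this point, so there is nothing to reproduce. The check compares the rules and then does simple arithmetic.

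**1. Rules side by side (SAP 3.2.1.1)**

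| Item | Target lesions present | Non-target disease only |
|---|---|---|
| Basis of the middle category | Sum of diameters | Qualitative non-target read, no new lesion |
| Name in the RECIST table | SD | Non-CR/Non-PD |
| Name in the SAP's BOR count | SD | SD |

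**2. Path into DCR.** Non-CR/Non-PD becomes SD in confirmed BOR if the 6-week minimum is met. It then enters the DCR numerator if it lasts at least 16 weeks. The denominator is the FAS. Unconfirmed BOR is relabelled too, but DCR does not use it.

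**3. Can such patients exist?** Yes. Part 1 entry does not require measurable disease. Both Protocol 10.4.1 and SAP 3.2 restrict the Part 1 OR endpoint to patients who have it. Neither document says how many do not.

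**4. Size on a fixed denominator.** Each non-target-only patient counted as SD for at least 16 weeks adds 1/n to DCR:

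- n = 3 (6 mg/kg Q2W, Protocol 3.2.4.1): 1/3 = 33.3 points
- n = 7 (9 mg/kg Q2W, Protocol 3.2.4.1): 1/7 = 14.3 points
- n = 34 (planned Part 1 size, Protocol 5.5): 1/34 = 2.9 points

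**5. Illustration under assumptions.** Let N be the FAS size, m the measurable-disease patients with disease control, u the non-target-only patients enrolled, and k those among the u who are counted through this rule. Assume that none of the u reaches CR.

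- SAP rule: (m + k)/N
- Separate category, same denominator: m/N
- Measurable disease only: m/(N − u)

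Take N = 34 and m = 3, both for illustration, with exact Clopper-Pearson 95% intervals where shown:

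| u | k | SAP rule | Same denominator | Measurable only |
|---|---|---|---|---|
| 0 | 0 | 3/34 = 8.8% | 3/34 = 8.8% | 3/34 = 8.8% |
| 3 | 3 | 6/34 = 17.6% (6.8–34.5) | 3/34 = 8.8% (1.9–23.7) | 3/31 = 9.7% (2.0–25.8) |
| 3 | 0 | 3/34 = 8.8% | 3/34 = 8.8% | 3/31 = 9.7% |

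**6. Direction.** On a fixed denominator the rule can only raise DCR. Against the measurable-disease DCR, the SAP's version is higher only if k/u exceeds m/(N − u), as the last row shows.

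**The case against.** The strongest points on the other side are these.

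- **The category list comes from the protocol.** Protocol 8.3.1 records each visit's response as PD, SD, PR, CR or NE, and Protocol 10.4.1 summarises BOR in the same five. The SAP had to place these patients somewhere. This explains the choice, but it does not answer the footnote, and nothing prevents an added row.
- **The footnote is advice.** It states a preference and does not prohibit. The SAP's rule is pre-specified and openly stated. Both are true, so this is a poor choice against a recommendation, not a concealed error.
- **The pooling can be undone.** Listings 16.2.6.7.1 to 16.2.6.7.4 give target lesions, non-target lesions, response by visit, and BOR and DCR by patient. All are marked for the abbreviated report. This stands, but Table 14.2.4.1, also marked, cannot show the split.
- **Little depends on DCR.** The primary endpoint is DLTs, the analyses are descriptive, and no decision rule uses DCR. This stands and limits the weight of the point.

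A reader might also infer that these patients' tumours were never assessed, or that disease control means only that nobody called unequivocal progression. The documents do not support that. They are scanned by CT or MRI on the same schedule, a new lesion also makes PD in Table 2, and the 6-week and 16-week minimums apply. Under Protocol Appendix 1, non-measurable disease includes lesions under 10 mm and nodes of 10 to under 15 mm. What is missing is a sum of diameters.

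**Conclusion.** The conflict in the text is clear: the SAP reproduces the RECIST advice and then does the opposite for both versions of BOR. The rule reaches DCR because DCR, unlike OR, is not limited to measurable disease. It warrants a correction to secondary descriptive endpoints. The DLT endpoint and OR are not touched.

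The size is conditional. It is zero if no patient with non-target disease only was enrolled. Otherwise it is 1/n per patient counted, on a fixed denominator. A reader might go further and infer a particular inflation of the overall DCR, for example by assuming that several of 34 patients qualify. The documents do not support any such figure. They give no count of these patients, and 34 is planned enrolment, whereas SAP 1 says enrolment was stopped during Part 1. The large steps in small groups are also a feature of any yes/no endpoint at those sizes. They show sensitivity to the rule, not that a shift occurred.

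**What to change.** 1. In SAP 3.2.1.1 and 4.10.2.1, make Non-CR/Non-PD a separate BOR category, added to the protocol's five, and remove it from the SD count for confirmed and unconfirmed BOR. Show it in Table 14.2.4.1 and Listing 16.2.6.7.4.
2. Report DCR in patients with measurable disease at baseline, restricting numerator and denominator alike.
3. Keep the all-FAS DCR as a sensitivity analysis, labelled as including Non-CR/Non-PD.
4. Record the added category in SAP 4.14 as a change from the protocol.

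No new data are needed, because SAP 3.2.1.1 already has non-target responses captured in the CRF. The cost is a change of wording, one extra row, a smaller denominator with correspondingly wider intervals, and a DCR that may be slightly less favourable.

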5.3.5 Schedule of Assessments

Schedule of Assessments are provided in Table 2 (Q1W dosing) and Table 3 (Q2W dosing).

Visit windows are included. The projection of visit days within each cycle must be made from Day 1 of the respective cycle. Furthermore, each new cycle must be initiated as soon as possible after completion of the previous cycle to maintain the dosing schedule.

All individual assessments are to be performed on or about the indicated visit day (i.e., ± 2 days) unless otherwise stated. All efforts should be made to perform assessments as close as possible to the scheduled time points.

Confidential Page 42 of 156

Table 2 Schedule of Assessments: Q1W Dosing

Pre-Treatment Period						Treatment Period ¹						Post-Treatn	nent Period ²				
	Screening			Cycle 1	l			Су	cle 2, 4,	6 etc.		(Cycle 3,	5, 7 etc		EOT	1M FUP
Day within Cycle Visit Window (± days)	D-14 to D-1	D1	D3	D8 (±2)	D15 (±2)	D22 (±2)	D1 (±2)	D8 (±2)	D15 (±2)	D22 (±2)	End of Cycle	D1 (±2)	D8 (±2)	D15 (±2)	D22 (±2)	≤ 10 d from the decision of trial treatment withdrawal	1 month after last dose of trial treatment (30+7d)
Informed Consent ³	X																
Baseline Characteristics ⁴ /Eligibility	X	X															
Safety Assessments																	
Medication/Procedure Survey	X	X	X	X	X	X	X	X	X	X	X	X	X	X	X	X	X
(S)AE Survey and Reporting	X	X	X	X	X	X	X	X	X	X	X	X	X	X	X	X	X
DLT Evaluation ⁵ Part 1 only		X	X	X	X	X	C2 only										
Vital Signs and Body Measurements	X	X		X	X	X	X	X	X	X		X	X	X	X	X	X
ECOG PS ⁶	X	X^6					X					X				X	X
Physical Examination ⁶	X	X^6					X					X				X	X
ECG ⁷	X															X	
ECHO or MUGA scan ⁸	X															X	
Safety blood samples ^{6,9}	X	X ⁶	X	X	X	X	X		X			X		X		X	X
Urinalysis ^{6,9}	X	X^6			X		X					X				X	X
Pregnancy Test	X															X	
Complement Panel ¹⁰ Part 2 only		X															
Disease Assessments																	
Disease Status Evaluation by CT/ MRI ^{11,12}	X										X					X^{12}	X^{12}
Tumor Marker Evaluation, if applicable ¹³	X										X					X	X
Archival Tumor Tissue ¹⁴ Part 1: Submit if available (optional)	X																
Additional Assessments																	
PK Samples ¹⁵		X	X	X	X	X	X	X	X	X		X	X	X	X	X	X
ADA Sample		X					C2 only					X				X	X
Skin Biopsy ¹⁶	X			X	X		-										
Tumor Biopsy ¹⁷																	
Part 1: Optional	X										C2 only						
Part 2: Required																	
Biomarker Blood Sample ¹⁸	X										C2 only					X	
Trial Treatment																	
Pan-HER Premedication ¹⁹		X		X	X	X	X	X	X	X		X	X	X	X		

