10.4.1 Efficacy Endpoints and Analyses

All statistical analysis of the secondary endpoints will be presented using the FAS.

The following anti-tumor response endpoints will be measured in Part 1:

• Documented OR, defined as documented PR or CR, from baseline to end of trial participation (in patients with measurable disease only)

The following anti-tumor response endpoints will be measured in Part 2:

- Changes in sum of diameters of target lesions from baseline to end of trial participation
- SD for >16 weeks from baseline
- Time to documented PD, death, patient withdrawal or end of trial participation, whichever comes first
- Overall survival (OS)

Best overall response by RECIST v1.1 will be summarized by trial part and cohort by means of counts and percentages for the categories CR, PR, SD, PD, and NE.

Number and percentages of patients with documented OR in the dose-escalation part will be presented including corresponding 95% exact Clopper-Pearson CI. All documented ORs (Part 1 and Part 2) will be listed including duration (in days) of OR, measured from time of first PR or CR to PD.

Duration of SD is calculated from baseline until first measurement of PD. The number and percentages of patients with SD for more than 16 weeks will be presented by trial part and tumor type.

Time to documented PD, death, patient withdrawal or end of trial participation, whichever comes first, will be presented in a Kaplan-Meier plot. The median progression free survival time, including 95% CI, will be derived. There will be one plot for Part 1, and plots for each of the 4 tumor types in Part 2.

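### The 16-week SD cutoff for DCR falls on the last day of the end-of-Cycle-4 scan window with no tolerance, so classification can turn on scan date rather than scan result

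*SAP*

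**What the plan says.** **Definition.** SAP 3.2.1.1 states: "The DCR is defined as the percentage of patients who had confirmed BOR of CR, PR or SD of at least 16 weeks". It then equates SD duration with TTP and says that "these times will be used to determine if a patient was in SD for at least 16 weeks".

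**Clock.** The printed TTP formula is the PD date minus "Date of first IMP infusion + 1) / 7", that is, study day divided by 7. A patient whose last assessment shows CR, PR or SD "will be censored at the time of last available tumor assessment per RECIST v1.1", and so does a patient who dies without documented PD.

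**Scan timing.** Scans are due at the end of Cycles 2, 4, 6 and so on. SAP 3.2.1.1 adds: "End of cycle assessments may be conducted at any time during the week prior to Day 1 of the next cycle". Protocol 5.3.5 says: "The projection of visit days within each cycle must be made from Day 1 of the respective cycle". Cycles last 28 days, with ±2 days on visits.

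**Protocol counterpart.** Protocol 10.4.1 lists "SD for >16 weeks from baseline" among the Part 2 endpoints and measures SD duration from baseline to the first PD. SAP 4.14 records that DCR was added and that duration of SD was dropped because it overlaps with TTP. It does not mention the change of threshold or of starting point.

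**The concern.** The cutoff coincides with the last permitted day of the scan that is meant to inform it. The SAP gives no tolerance for the scan window, and nothing in it requires SD to be observed at or near week 16. Two patients with the same result at the same scheduled scan can be classified differently because one was scanned a few days earlier. A patient stable at the 16-week scan can be left out of disease control, and a patient progressing at that scan can be counted in.

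DCR is a listed secondary efficacy endpoint. SAP 4.10.2.1 reports it by regimen and dose level with exact 95% intervals, and Table 14.2.4.1 and Listing 16.2.6.7.4 are both marked for the abbreviated report. In small cohorts a single patient visibly changes the estimate.

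**Working it through.** The plan states no figure for this rule, so there is none to reproduce. The check is calendar arithmetic.

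**Inputs**
- Cycle of 28 days, ±2 days (Protocol 5.3, Table 1).
- Scan in the 7 days before Day 1 of the next cycle, every second cycle (SAP 3.2.1.1).
- TTP in weeks = study day / 7, with day 1 the first infusion (SAP 3.2.1.1).
- Minimum SD of 6 weeks for a best overall response of SD (SAP 3.2.1.1).
- One-month follow-up (1M FUP) visit 30 (+7) days after the last dose (Protocol 5.3.4), with a scan if PD was not documented by end of treatment (SAP 3.2.1.1).
- Patients entered per level: 1, 1, 4, 3, 7 and 3 (Protocol 3.2.4.1, as of Amendment 6).

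**Step 1: scan windows.** Day 1 of cycle k+1 = 28k + 1.
- After Cycle 2: next Day 1 is day 57, window days 50–56, or 7.14–8.00 weeks. SD here already meets the 6-week minimum.
- After Cycle 4: next Day 1 is day 113, window days 106–112.
- After Cycle 6: next Day 1 is day 169, window days 162–168, or 23.14–24.00 weeks.

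**Step 2: SD at the end-of-Cycle-4 scan, with no later scan**

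| Study day | 106 | 107 | 108 | 109 | 110 | 111 | 112 |
|---|---|---|---|---|---|---|---|
| Weeks | 15.14 | 15.29 | 15.43 | 15.57 | 15.71 | 15.86 | 16.00 |
| At least 16? | no | no | no | no | no | no | yes |

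Six of 7 days fail. If Day 1 of Cycle 5 shifts by −2, −1, 0, +1 or +2 days, the number of passing days is 0, 0, 1, 2 or 3 of 7.

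**Step 3: SD at the end of Cycle 2, then PD at the next scan.** PD on day 111 gives 111/7 = 15.86 weeks, not controlled. PD on day 112 gives 16.00 weeks, controlled, with no delay at all. After delay, PD on day 113 gives 16.14 weeks and PD on day 119 gives 17.00 weeks, both controlled.

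**Step 4: the scan that can rescue Step 2.** The last Cycle 4 dose is on day 84 + 22 = 106 (Q1W) or 84 + 15 = 99 (Q2W). The 1M FUP scan then falls on days 136–143 (19.43–20.43 weeks) or 129–136 (18.43–19.43 weeks). Either exceeds 16 weeks, whatever it shows.

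**Step 5: weight of one patient.** 1/7 = 14 points, 1/4 = 25 points, 1/3 = 33 points. The 1 and 2 mg/kg levels had one patient each.

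**The case against.** **Running SD to the PD date is prespecified.** Protocol 10.4.1 measures SD duration to the first PD, so a reader who infers that counting time up to PD is itself an error goes too far. This stands. The weakness is pairing that convention with a fixed cutoff on the edge of a scan window.

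**The 1M FUP scan usually lifts a patient with SD at Cycle 4 over 16 weeks.** This also stands. A reader might infer that most such patients are lost; the documents do not support that. The failure is confined to patients with no later scan.

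**The protocol's stricter threshold.** One might infer that under more than 16 weeks all 7 window days fail. That puts the protocol's threshold on the SAP's clock. The protocol counts from baseline, and the baseline scan may be up to 28 days before Day 1. By simple date difference, a baseline scan 8 days before the first infusion puts a day-106 scan at 105 + 8 = 113 days, above 112.

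**Dose delay.** One might also infer that a set total of delay triggers the PD case, or that toxic dose levels systematically gain apparent control. Delay is not needed, since PD on day 112 passes on schedule. A delay within a cycle need not move the next Day 1 by the same amount, because Protocol 5.3.5 asks for each cycle to start as soon as possible to keep to schedule. Suspected PD also prompts an immediate scan. Delay can push a PD scan past the cutoff, but no figure in the documents sizes any toxicity-related bias.

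**Low stakes.** All analyses are descriptive, Part 2 did not take place, and per-patient response, TTP and DCR are listed, so borderline cases can be seen. This limits the harm but does not settle the rule. The patient-by-patient review in SAP 3.2.1.1 covers time-point and best overall responses, not the 16-week cutoff.

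**Conclusion.** The concern holds as a derivation gap in a descriptive secondary endpoint. SD at the end-of-Cycle-4 scan, when it is the last available assessment, fails on 6 of 7 nominal days. SD seen only at the end of Cycle 2, with PD first seen on day 112 or later, passes. One patient is worth 14 to 33 points in the cohorts of 3 to 7.

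This rests on three assumptions:
- Nominal 28-day cycles, tested with a shift of up to 2 days in Day 1 of Cycle 5.
- Use of the censored TTP time for patients still in SD. The SAP implies this, but the printed formula shows only the PD date.
- Cohort sizes as of Amendment 6.

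How many patients are affected cannot be known from the documents. A cheap correction is worthwhile; the gap does not undermine the trial's primary analysis.

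**What to change.** In SAP 3.2.1.1, for a best overall response of SD, define 16-week control from the scan result. The patient should have CR, PR, SD or non-CR/non-PD either:
- at the scheduled end-of-Cycle-4 scan, on any day of its permitted window including the Day 1 visit tolerance; or
- at any later scan, including an end-of-treatment or 1M FUP scan, on or after nominal day 106.

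There should be no PD on or before that assessment. State the tolerance explicitly, and state that the censored TTP time is not used as the cutoff. Tying the first condition to the scheduled scan matters: if Day 1 of Cycle 5 is 2 days early, the window is days 104–110, and a bare day-106 floor would create a new edge.

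In SAP 4.14, record the change from the protocol's threshold of more than 16 weeks from baseline.

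The cost is one paragraph, one derivation and one line in SAP 4.14, with no new data. The downside is that scans about a week before the nominal 16-week mark are accepted.
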